9.4.1.3. Primary and Secondary Analyses

The proportion of responders will be analyzed using CMH tests [REDACTED]. In addition, 2-sided 95% confidence intervals for the treatment differences in response rates will be provided. Between group comparisons will only be performed for each BOTOX group against the placebo group, and BOTOX high dose group against the BOTOX low dose group.

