#### 11.0 EFFICACY ANALYSES

The efficacy analyses will be based on the mITT population. Observed data will be used for all analyses. Baseline for efficacy is defined as the last non-missing efficacy assessment before study intervention.

The following set of hypotheses will be used to compare the BOTOX groups with placebo for the primary endpoint analysis:

 Null hypothesis: BOTOX and placebo are equally effective in the probability of achieving ≥ 1-grade improvement in the C-APPS score from baseline at Day 14.

 Alternative hypothesis: BOTOX and placebo are not equally effective in the probability of achieving ≥ 1-grade improvement in the C-APPS score
 from baseline at Day 14.

The following set of hypotheses will be used to compare the BOTOX groups with placebo for the secondary endpoint analysis:

- Null hypothesis: BOTOX and placebo are equally effective in the probability of achieving ≥ 1-grade improvement in the P-APPS score from baseline at Day 14.
- Alternative hypothesis: BOTOX and placebo are not equally effective in the probability of achieving ≥ 1-grade improvement in the P-APPS score
   from baseline at Day 14.

For the primary endpoint analysis, the Cochran-Mantel Haenszel (CMH) test will be used to evaluate the equality of responder proportions of C-APPS between study intervention groups.

The BOTOX high dose group will be compared to the placebo group, and the BOTOX low dose group will be compared to the placebo group using a gate-keeping strategy (Dmitrienko 2005). If the comparison of the BOTOX high dose group versus the placebo group yields a p-value at the 0.05 significance level, the BOTOX low dose group will then be compared with the placebo group at the same 0.05 significance level. Otherwise, the BOTOX low dose group will not be considered statistically significantly superior to the placebo group, regardless of its p-value. (see Section 11.3.)

Similarly, for the secondary endpoint analysis, the statistical comparisons will be conducted for the P-APPS.

All statistical tests will be 2-sided hypothesis tests performed at the 0.05 level of significance for main effects. Wald confidence intervals for proportions of responders and difference in the proportion of responders will also be presented. All confidence intervals will be 2-sided 95% confidence intervals.

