Continuous descriptive statistics include the following: the numbers of participants with non-missing values at both baseline and the specified post-baseline analysis visit, mean, SD, median, minimum, and maximum.

Categorical variables will be summarized by number and percentage of participants.

Efficacy analyses will be performed for all visits. The primary analysis timepoint is Day 14.

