#### 11.1 PRIMARY EFFICACY ENDPOINTS

The primary efficacy endpoint will be a	chievement of a $\geq$ 1-grade C-APPS improvemen
from baseline	on Day 14.

The evaluation of the equality of the proportions of responders will be based on the CMH test

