#### 13.0 INTERIM ANALYSIS

No interim analysis is planned for this study.

Approximately 165 participants will be enrolled in a 1:1:1 randomization allocation ratio, yielding approximately 55 participants in the BOTOX high dose group, 55 participants in the BOTOX low dose group, and 55 participants in the placebo group. With an anticipated attrition rate of approximately 10%, approximately 148 participants will be analyzable for the primary endpoint.

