### 16.0 DATA HANDLING CONVENTIONS

### 16.1 VISIT DAY WINDOWS

Table 16-1 presents the visits assigned for efficacy analyses and the corresponding range of study days (window) during which an actual visit may occur.

Table 16-1 Visit Day Windows

Derived Visit	Scheduled Visit Day a	Analysis Window
Baseline	Day 1	-
Day 7	Day 7	Days [2, 10]
Day 14	Day 14	Days [11, 21]
Day 30	Day 30	Days [22, 45]
Day 60	Day 60	Days [46, 75]
Day 90	Day 90	Days [76, 105]
Day 120	Day 120	Days 106 to study exit

a Relative to the date of the first dose of intervention. Day 1 is defined as the date of the first dose of study intervention. There is no Day 0 or Week 0.

If the assessment date (if unavailable, use visit date instead) is on or after the date of the first dose of study intervention, the study day is calculated by (assessment date – date of the first dose of study intervention + 1). If the assessment date is before the date of the first dose of study intervention, the study day is calculated by (assessment date – date of the first dose of study intervention). Therefore, a negative day indicates a day before the start of the study intervention.

If there are values from multiple visits in a given window, the value collected from the visit closest to the scheduled visit day will be used to represent the window. If two visits are equidistant from the scheduled visit day, the latter non-missing value will be used to represent the visit assessment.

If multiple unscheduled visits occur on the same day, but no collection times are available, the most conservative (ie, worst) values will be used for each parameter separately.

However, the P-APPS for the baseline analysis visit must be completed prior to or on Day 1; otherwise, the P-APPS for baseline/Day 1 visit will be considered missing.

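### Minor, reporting only: the planned Wald 95% intervals cover somewhat less than 95% at about 49 per arm, most clearly for single arms near 0% or 100% and at the lower limit of the difference when BOTOX rates are high

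*SAP*

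**What the plan says.** SAP 11.0 fixes the interval method: "Wald confidence intervals for proportions of responders and difference in the proportion of responders will also be presented". It adds: "All confidence intervals will be 2-sided 95% confidence intervals". The readable text names no continuity correction, no alternative interval and no rule for an arm with 0% or 100% responders.

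Protocol 9.4.1.3 promises that "2-sided 95% confidence intervals for the treatment differences in response rates will be provided". Its readable text names no method, so the SAP does not contradict it.

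The intervals decide nothing. SAP 11.1 says: "The evaluation of the equality of the proportions of responders will be based on the CMH test". The serial gatekeeping table (protocol Table 9-3, SAP Table 11-1) works on p-values alone.

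On size, the SAP's sample-size text expects that "approximately 148 participants will be analyzable for the primary endpoint". On scope, SAP 11.0 says "Efficacy analyses will be performed for all visits", and Table 16-1 in SAP 16.1 defines six post-baseline visits.

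**The concern.** The Wald interval takes its standard error from the observed proportion. With about 49 participants this has three consequences:

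- **Zero width at the edges.** Near 0% or 100% the standard error is too small. At exactly 0/n or n/n it is zero.
- **One-sided error in the difference.** With a high BOTOX rate and a low placebo rate, the excess misses fall on the lower limit, in the direction that flatters the product.
- **Disagreement with the test.** Wald uses an unpooled variance and CMH a pooled one. An interval can therefore exclude zero beside a non-significant p-value.

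Only the accuracy of the intervals printed beside the p-values is at stake. In a dose-ranging Phase 2 trial, though, those intervals are what readers use to judge effect size. If responder intervals are shown at every post-baseline visit, there would be 3 arms × 2 scales × 6 visits = 36 single-arm intervals, and some could sit at extreme rates.

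**Working it through.** **Inputs.** There are 165 participants randomized 1:1:1 with 10% attrition (protocol 4.1 and 9.2; SAP sample-size text). Intervals are Wald, 2-sided 95% (SAP 11.0). Analyses use observed data, so the denominator is the observed n. Responder rates are not readable, so those below are assumptions.

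**The plan's own figure.** 165 × (1 − 0.10) = 148.5, which matches the stated 148. Per arm, 148 / 3 = 49.3. Sizes 44 to 56 were also run, because coverage oscillates with n.

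**Formulas.**
- Wald, one arm: p̂ ± 1.96 √[p̂(1 − p̂)/n].
- Wald, difference: p̂₁ − p̂₂ ± 1.96 √[p̂₁(1 − p̂₁)/n₁ + p̂₂(1 − p̂₂)/n₂].
- Coverage: the sum of exact binomial probabilities over all outcomes whose interval contains the truth. Lower miss: the same sum where the lower limit exceeds the truth (nominal 2.5%).
- Miettinen-Nurminen: all δ for which (p̂₁ − p̂₂ − δ)² ≤ 1.96² × [p̃₁(1 − p̃₁)/n₁ + p̃₂(1 − p̃₂)/n₂] × N/(N − 1). Here p̃₁ and p̃₂ are the maximum-likelihood estimates constrained to p̃₁ − p̃₂ = δ.

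**Difference, placebo 10%.** Cells show coverage (lower miss). The last two columns average all 169 arm-size pairs from 44 to 56.

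| BOTOX | Wald, 49 v 49 | Wald, averaged | Miettinen-Nurminen lower / upper miss, averaged |
|---|---|---|---|
| 50% | 94.4% (3.1%) | 94.3% (3.3%) | 2.4% / 2.6% |
| 70% | 93.1% (5.1%) | 94.0% (4.2%) | 2.1% / 2.8% |
| 80% | 92.1% (6.2%) | 93.6% (5.0%) | 2.0% / 3.0% |
| 90% | 92.7% (6.5%) | 92.8% (6.1%) | 1.7% / 3.2% |

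Miettinen-Nurminen coverage in these four settings averages 95.0–95.1%.

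Over a grid at n = 49 with BOTOX 70–90% and placebo 5–30%, Wald averages 93.7% coverage with a lower miss of 4.7%. Miettinen-Nurminen averages 95.1% and 2.0%. With BOTOX 30–70% and placebo 5–29%, the averages are 94.3% and 95.0% coverage.

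**Worked example, 39/49 v 5/49.** The difference is 0.796 − 0.102 = 0.694. The standard error is √(0.796 × 0.204/49 + 0.102 × 0.898/49) = 0.072. Wald gives 0.694 ± 0.141, or 55.3% to 83.5%. Miettinen-Nurminen gives 52.7% to 81.0%.

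**Single arm.** Coverage at n = 49 (range over n = 44 to 56):

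| True rate | Wald | Wilson |
|---|---|---|
| 2% or 98% | 62.8% (58.9–67.7%) | 92.5% (91.8–98.0%) |
| 10% or 90% | 87.2% (86.4–95.0%) | 97.3% (93.4–97.3%) |
| 20% or 80% | 93.4% (90.6–95.3%) | 95.3% (93.5–96.5%) |

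Nearly all of the shortfall at 2% is the chance of 0/49, which is 0.98⁴⁹ = 37%. That chance is 0.95⁴⁹ = 8.1% at a true 5% and 0.90⁴⁹ = 0.6% at 10%. For 0/49, Wald is 0 to 0, while the Wilson upper limit is 1.96²/(49 + 1.96²) = 7.3%.

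**Agreement with CMH, one stratum, 49 v 49.** Of the 50 × 50 = 2500 possible tables, 20 have a Wald interval that excludes zero with CMH p > 0.05 (p from 0.0507 to 0.0556). The chance of such a table is 2.5% at 30% v 10%, 2.9% at 40% v 20% and 0.07% at 50% v 10%. It is negligible at 70% v 10% and above. Miettinen-Nurminen has no such table: at δ = 0 its statistic and the one-stratum CMH statistic both equal (N − 1)n₁n₂(p̂₁ − p̂₂)²/[m(N − m)], where m is the total number of responders.

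**The case against.** The strongest reply is that the plan contains no error. It names a standard method in advance, agrees with the protocol and rests every decision on CMH. Statisticians also differ on the best replacement; Newcombe or Agresti-Caffo intervals would serve too. All of that is true, and it is why the point is minor.

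Four further objections limit the size of the effect:

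- **Rates.** The lower-limit excess matters at BOTOX rates of about 70% or more. The planned rates and part of the responder definition are not readable, so nobody outside can say whether that applies.
- **Plain Wald is assumed.** With a continuity correction, mean coverage of the difference would be 96.4–96.8%, with a lower miss of about 2.8% at BOTOX 70–90%. A single arm at 2% would still have 62.8%. The readable SAP names no correction.
- **Unfavourable n.** n = 49 is the low point for 80% v 10%, and near the low end for a single arm at 10%. Averaged over n = 44 to 56, those become 93.6% and 90.8%. The shortfall shrinks but remains.
- **Visits.** SAP 11.4 specifies only descriptive statistics at all visits, so the 36 single-arm intervals are a possibility and not a certainty.

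The replacement is not perfect either: Miettinen-Nurminen moves some misses to the upper limit, and Wilson is not exactly nominal at extreme rates. Averaged over arm sizes, however, Miettinen-Nurminen comes out at 95% where Wald does not.

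**Conclusion.** The concern holds as a minor reporting point. Under plain, unstratified, uncorrected Wald at about 49 per arm:

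- For the difference, the average shortfall is under 1 point at mid-range rates, which is negligible.
- If BOTOX rates are 80–90% against about 10% on placebo, the lower limit is too high about 4–8% of the time across equal arm sizes of 44 to 56, against a nominal 2.5%.
- Single-arm intervals are clearly too short near 0% or 100%, and have zero width at 0/n or n/n.

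The CMH p-values, type I error, power and gatekeeping order are unaffected. The arithmetic is firm. Whether the high-rate case arises depends on rates that the public text does not show. Any CMH strata are not readable, so no defect in stratification is alleged.

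**What to change.** Replace the Wald sentence in SAP 11.0 with:

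> Wilson (score) 95% CIs will be given for each responder proportion and Miettinen-Nurminen (score) 95% CIs for the differences, using the same strata, if any, as the CMH test (Mantel-Haenszel weights if stratified).

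The cost is one sentence and a small programming change, and protocol 9.4.1.3 needs no amendment. The downsides are modest:

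- The intervals are not symmetric about the estimate.
- Miettinen-Nurminen upper-limit misses run at about 3–4% when BOTOX rates are high.
- Wilson coverage at n = 49 is 97.3% at a true 10% and 92.5% at 2%.

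The stratified form was compared with stratified CMH in 60,000 simulated trials (three assumed stratum layouts, 20,000 each), with no disagreement. Those layouts are assumptions, so the sponsor should confirm the result with the actual strata.

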#### 11.1 PRIMARY EFFICACY ENDPOINTS

The primary efficacy endpoint will be a	chievement of a $\geq$ 1-grade C-APPS improvemen
from baseline	on Day 14.

The evaluation of the equality of the proportions of responders will be based on the CMH test

### 11.2 SECONDARY EFFICACY ENDPOINTS

The secondary efficacy endpoint will be achievement of  $\geq$  1-grade P-APPS improvement from baseline on Day 14, as rated at maximum contraction by the participant using the P-APPS.

# 11.3 MULTIPLE COMPARISONS PROCEDURE FOR PRIMARY AND SECONDARY ENDPOINTS

The overall familywise error rate (FWER) will be controlled at  $\alpha = 0.05$  for the set of primary and secondary endpoint comparisons between each of the BOTOX groups versus placebo. The overall serial gatekeeping multiple comparisons procedure (MCP) is defined as follows:

Table 11-1 Multiple Comparisons Procedure

MCP Step a	Endpoint	MCP Criteria
1	C-APPS responder (BOTOX high dose vs placebo)	Nominal p-value $\leq \alpha$
2	P-APPS responder (BOTOX high dose vs placebo)	Nominal p-value $\leq \alpha$
3	C-APPS responder (BOTOX low dose vs placebo)	Nominal p-value $\leq \alpha$
4	P-APPS responder (BOTOX low dose vs placebo)	Nominal p-value $\leq \alpha$

<sup>a Serial gatekeeping MCP only proceeds to next step if all endpoints are statistically significant after application of MCP criteria in previous and current MCP steps for a BOTOX group.

#### 11.4 ADDITIONAL EFFICACY ENDPOINTS

Categorical and continuous descriptive statistics, including change from baseline, will be presented for all visits for C-APPS and P-APPS scores. Continuous descriptive statistics will be provided for all visits

Methods for analyzing additional PRO endpoints aside from the P-APPS will be described and summarized in a separate analysis plan and report.

### 12.0 SAFETY ANALYSES

The safety analyses will be performed using the safety population. The safety parameters will include adverse events (AEs) and vital signs. For vital signs, the last non-missing safety assessment before the first dose of study intervention will be used as the baseline.

Continuous variables will be summarized by number of participants, mean, SD, median, minimum, and maximum values. Categorical variables will be summarized by number and percentage of participants.

### 12.1 ADVERSE EVENTS

AEs will be coded by SOC and PT using MedDRA version 23.0 (or newer).

An AE will be considered a treatment-emergent adverse event (TEAE) if the AE began or worsened (increased in severity or became serious) on or after the date (and time, if known) of the first dose of study intervention. Per case report form instructions, a new AE record will be created with a new AE onset date for any AE that worsens. Therefore, TEAEs can simply be identified as those AEs with recorded onset date (and time, if known) on or after the date (and time) of intervention injection.

Procedure-related AEs due to injection are identified as, but not limited to, the following: localized pain, inflammation, paresthesia, hypoesthesia, tenderness, swelling/edema, erythema, localized infection, bleeding, and/or bruising. In addition, needle-related pain and/or anxiety have resulted in vasovagal responses, including transient symptomatic hypotension and syncope.

If more than 1 AE is coded to the same PT for the same participant, the participant will be counted only once for that PT using the greatest severity and strictest causality for the summarization by severity and causal relationship. An AE will be considered a serious TEAE if it is a TEAE that additionally meets any serious AE criteria.

The total number and percentage of participants reporting AEs, TEAEs, treatment-related TEAEs (ie, study drug-related TEAEs, study procedure-related TEAEs), serious TEAEs, treatment-related serious TEAEs, deaths, AESIs, PDSOTs, and discontinuations due to TEAEs will be summarized for each study intervention group.

The number and percentage of participants reporting TEAEs will be summarized in descending order by SOC and PT for each study intervention group. In addition, TEAEs will also be summarized in descending order by PT for each study intervention group.

The number and percentage of participants reporting treatment-related TEAEs will be summarized in descending order by PT for each study intervention group.

In addition, severity of TEAE will be summarized by PT for each study intervention group.

For the safety population, separate listings will be presented for all AEs, participants who died, serious AEs (SAEs), AEs leading to study discontinuation, and pretreatment AEs (ie, AEs that occur after signing of the informed consent and prior to first dose of study medication).

12.3	POSSIBLE DISTANT SPREAD OF TOXIN (PDSOT)
	All TEAEs associated with be tabulated by SOC, PT, and study intervention group; in addition, all Es will be listed by participant.

## 12.4 CLINICAL LABORATORY PARAMETERS

[figure not shown]
A listing for positive pregnancy test results will be provided, including study intervention group, urine sample collection date, and date of study intervention administration.

## 12.5 VITAL SIGNS

Descriptive statistics for vital signs (systolic and diastolic blood pressures, respiratory rate, and pulse rate) and changes from baseline values at each study assessment visit will be presented by study intervention group.

#### 13.0 INTERIM ANALYSIS

No interim analysis is planned for this study.

Approximately 165 participants will be enrolled in a 1:1:1 randomization allocation ratio, yielding approximately 55 participants in the BOTOX high dose group, 55 participants in the BOTOX low dose group, and 55 participants in the placebo group. With an anticipated attrition rate of approximately 10%, approximately 148 participants will be analyzable for the primary endpoint.

## 15.0 STATISTICAL SOFTWARE

Statistical analyses will be performed using SAS version 9.4 (or newer) on a Linux operating system.

### 16.0 DATA HANDLING CONVENTIONS

### 16.1 VISIT DAY WINDOWS

Table 16-1 presents the visits assigned for efficacy analyses and the corresponding range of study days (window) during which an actual visit may occur.

Table 16-1 Visit Day Windows

Derived Visit	Scheduled Visit Day a	Analysis Window
Baseline	Day 1	-
Day 7	Day 7	Days [2, 10]
Day 14	Day 14	Days [11, 21]
Day 30	Day 30	Days [22, 45]
Day 60	Day 60	Days [46, 75]
Day 90	Day 90	Days [76, 105]
Day 120	Day 120	Days 106 to study exit

a Relative to the date of the first dose of intervention. Day 1 is defined as the date of the first dose of study intervention. There is no Day 0 or Week 0.

If the assessment date (if unavailable, use visit date instead) is on or after the date of the first dose of study intervention, the study day is calculated by (assessment date – date of the first dose of study intervention + 1). If the assessment date is before the date of the first dose of study intervention, the study day is calculated by (assessment date – date of the first dose of study intervention). Therefore, a negative day indicates a day before the start of the study intervention.

If there are values from multiple visits in a given window, the value collected from the visit closest to the scheduled visit day will be used to represent the window. If two visits are equidistant from the scheduled visit day, the latter non-missing value will be used to represent the visit assessment.

If multiple unscheduled visits occur on the same day, but no collection times are available, the most conservative (ie, worst) values will be used for each parameter separately.

However, the P-APPS for the baseline analysis visit must be completed prior to or on Day 1; otherwise, the P-APPS for baseline/Day 1 visit will be considered missing.

# 16.2 REPEATED OR UNSCHEDULED ASSESSMENTS OF SAFETY PARAMETERS

If a participant has repeated assessments before the first dose of study intervention, the results from the final non-missing assessment made prior to the start of the study intervention administration will be used as baseline. If end-of-study assessments are repeated or if unscheduled visits occur, the last non-missing postbaseline assessment will be used as the end-of-study assessment for generating summary statistics. All assessments will be presented in the data listings.

## 16.3 MISSING SEVERITY ASSESSMENT FOR ADVERSE EVENTS

If severity is missing for an AE that started before the date of the first dose of study intervention, an intensity of mild will be assigned. If severity is missing for an AE that started on or after the date of the first dose of study intervention, an intensity of severe will be assigned. The imputed values for severity assessment will be used for the incidence summary; the values will be shown as missing in the data listings.

# 16.4 MISSING CAUSAL RELATIONSHIP TO STUDY TREATMENT FOR ADVERSE EVENTS

If the causal relationship to the study intervention is missing for an AE that started on or after the date of the first dose of study intervention, a causality of *yes* will be assigned. The imputed values for causal relationship to study intervention will be used for the incidence summary; however, the values will be shown as missing in the data listings.

## 16.5 MISSING DATE INFORMATION FOR ADVERSE EVENTS

Completely missing dates will not be imputed.

The following imputation rules only apply to cases in which the start date for AEs is incomplete (ie, partly missing).

### Missing month and day

- If the year of the incomplete start date is the same as the year of the first dose of study intervention, the month and day of the first dose of study intervention will be assigned to the missing fields
- If the year of the incomplete start date is before the year of the first dose of study intervention, *December 31* will be assigned to the missing fields
- If the year of the incomplete start date is after the year of the first dose of study intervention, *January 1* will be assigned to the missing fields

